Multi-centre prospective observational study of diagnosis, management and outcome in a large cohort of pregnancies affected by abnormal fetal brain development.

The study is designed to include all developmental brain abnormalities identified by ante-natal ultrasound screening from 18 weeks gestation onwards. Participants are recruited from at least 13 sites within the UK incorporating a wide geographic and socioeconomic base. MR scanning is then carried out either in a primary unit (Sheffield) or in one of five secondary units (Newcastle, Leeds, Birmingham, Belfast and Manchester). Figure 1 outlines the study design and length of time that each participant may remain in the study process.

Figure 1. MERIDIAN study design

Primary Outcomes

- 1) Absolute diagnostic accuracy of MR as assessed by percentage of cases where in utero MR diagnosis agrees with post-mortem autopsy/MR or postnatal imaging.
- 2) Absolute diagnostic accuracy of US as assessed by percentage of cases where US diagnosis at the time of referral for MR agrees with post-mortem autopsy/MR or postnatal imaging.

Agreement between prenatal diagnosis (both before and after MR) and outcome diagnosis will be judged by an appointed independent expert panel consisting of a fetal medicine clinician, paediatric neuroradiologist and paediatric neurologist or neurosurgeon.

Secondary Outcomes

Effect of including MR scan on diagnostic confidence

Change in diagnostic confidence will be measured before and after the MR scan as assessed by a 5 point Likert scale.

Effect of including MR scan on prognosis

Change in prognosis will be measured before and after the MR scan as assessed by a 4 point categorical scale (poor – less than 50% chance of normal neuro-developmental outcome, intermediate - 50-90% chance of normal outcome, favourable - greater than 90% chance of normal outcome, normal – no abnormality found after detailed fetal medicine investigation).

Effect of including MR scan on management

Change in management will be measured before and after the MR scan as assessed by a 2 point categorical scale. This scale will record whether termination of pregnancy was discussed on the basis of poor neuro-developmental prognosis.

4. Ancillary sub-studies

Sociological Study

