There are 3 distinct projects within this follow-up study, the aims and objectives have been divided by project to clearly demonstrate how they will be implemented:

Project 1:

The aim of project 1 is to refine our estimates of diagnostic accuracy of MR imaging as a technology to aid the prenatal diagnosis of fetal developmental brain abnormalities.

- 1) We will reassess the diagnostic accuracy of MR imaging compared to antenatal US through:
 - a) Measurement of diagnostic accuracy of antenatal US alone (i.e. prior to iuMR) relative to updated reference diagnosis at 2-3 years of age (post-natal imaging or post-mortem examination);
 - b) Measurement of diagnostic accuracy of iuMR (following antenatal US) relative to the updated reference diagnosis at 2-3 years of age (post-natal imaging or post-mortem examination).

Project 2:

The aim of project 2 is to improve the prognostic information available during pregnancy based on the functional and developmental outcomes of the MERIDIAN cohort.

- 1) We will quantify the value of prognoses based on MR imaging and on USS by:
 - a) Assessing the concordance between severe neurodevelopmental impairment (defined by BSID score of <80 on the Cognitive AND language index or a combined score of <85 or a motor score of <70, evidence of severe disability based on a score <-2SDs for the ASQ, or evidence of cerebral palsy based on GMFCS) and poor prognosis, based on MR and on USS;
 - b) Comparing the relative prognostic accuracy of USS and MR imaging;
- 2) We will qualitatively assess the cases for which the USS prognosis and MR prognosis differed, in relation specifically to the original diagnoses;
- 3) We will look at the concordance in the subgroup of children for which the MR scan was performed within 24 weeks;
- 4) We will assess ability to predict non-severe impairment (defined as BSID <85 or a score between 1 and 2 SDs for the ASQ).

Project 3:

The aim of project 3 is to assess the clinical significance of isolated, mild ventriculomegaly.

- 1) We will assess the clinical significance through:
 - a) Identification of all isolated, mild ventriculomegaly cases diagnosed on in utero MR in the MERIDIAN cohort and define their developmental outcome at 2-3 years (as per project 2);
 - b) Comparison of developmental outcome to the prognoses made based on USS.

3. Study design

Multi-centre observational cohort study of diagnostic accuracy and functional development of children born from the MERIDIAN study.

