Where it is not possible to arrange a face to face appointment, or if for any reason the questionnaires are not completed during the appointment then there will be the option for the GMFCS questions (adapted for parent completion) and SDQ to be posted out or given to parents for them to complete and return to the research team. Alternatively the questionnaires can be completed over the telephone with the child's parent.

The research team will categorise the children as severely impaired (scoring <70), mild-moderately impaired (scoring 70-85) or normal (scoring 85+) based on the results of the developmental assessments. These categories will be used to complete the developmental assessment CRF.

After the developmental assessments all participants will be debriefed via a feedback letter from the research team, which will contain details of the results from the developmental assessment. Where an important previously unrecognised disability has been identified, we will speak to parents about future actions. Typically this would include informing the GP and advising about appropriate referrals either to community paediatrics or therapy services. A member of the study team (NE, an experienced paediatrician) would be available for discussion and advice if the best course of action was not immediately apparent.

Project 3

There is no input required from the MERIDIAN participants or research sites for completion of project 3. Project 3 will be completed by the central study team at the University of Sheffield.

[figure not shown]
The information for project 3 will come from the assessments described in project 2. We will identify all cases of isolated mild ventriculomegaly diagnosed on iuMR and define their developmental outcome at 2-3 years as severely impaired, mild-moderately impaired or normal as per project 2. In MERIDIAN, the most common information given to women on the basis of isolated mild VM on USS is "favourable (90%)" followed by poor or intermediate and the remainder as normal.

We will calculate the prevalence of severe and non-severe impairments in isolated mild VM cases.

Please see Figure 2. for details of procedures and data collection document

Figure 2. Procedure for MERIDIAN 2-3 year follow up study

Screening

Project 1 – Case note review

Project 1 and 2 – Case note review and BSID

Project 1
If consented to project 1 only research midwife will conduct medical case note review and record details of any further follow up

Project 1 and 2

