Our sample size is constrained by the original MERIDIAN cohort, but our data collected to date provides some assurance that we will have adequate power to address the primary outcome defined by this project. As well as approaching all children known to have survived (expected number approximately 500), our analysis will include non-surviving infants (defined as having had poor outcomes; expected number approximately 50-100). Allowing for attrition in the surviving child group we approximate that there will be 400 cases, from data collected in the entire cohort, there are almost 200 instances where prognosis changed as a result of MR imaging, of whom 38 are now classified as the poorest prognosis. Scaling these prevalence's down, 400 cases will have a 90% power to detect a 20% increase in the sensitivity and a 10% increase in specificity using the tests outlined above at a two-sided significance level of 5%.

We will quantify the impact of selective participant retention by comparing prognoses and diagnoses of consenting participants with those who refused. Non-surviving fetuses or children will by definition have no BSID outcome data, but will be included in the primary analyses as having poor outcomes. Outcomes among fetuses for whom TOP was performed are controversial, but some diagnoses (for example TOP for anencephaly) are inevitably fatal. For these cases we will use our existing independent expert panels to adjudicate whether, and how, the data should be included.

Hypothesis

The clinical significance of fetal brain abnormalities are more accurately predicted by MR imaging when compared with USS. Specifically, we predict a 10% improvement in prognostic accuracy by using MR imaging.

Analysis of Project 3

Using the categories detailed in project 2 (severely impaired, mild-moderately impaired and normal) we will calculate the prevalence of severe and non-severe impairments from our data, together with exact binomial confidence intervals and compare this to the prognoses obtained from cases where USS identified isolated mild VM. Where prognosis changed as a result of MR imaging we will assess whether this was attributable to the MR identifying further diagnoses.

Sample size Project 3

With approximately 140 cases and assuming the prevalence of poor outcome is indeed less than 10%, we will be able to estimate the prevalence to within a standard error of 2.5%.

Hypothesis

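### Project 3's hypothesis is about excess risk over the general population, but its stated analysis compares impairment prevalence only with ultrasound prognoses, whose meaning of normal differs from the follow-up cut-off of 85

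*Protocol*

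**What the plan says.** All Project 3 text is in the 2-3 year follow-up protocol.

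- **Hypothesis** (section 7, after Sample size Project 3): isolated mild ventriculomegaly confirmed by MR carries no increased risk of poor neurodevelopmental outcome relative to the general population.
- **Analysis of Project 3** (section 7): the prevalence of severe and non-severe impairment is to be calculated with "exact binomial confidence intervals and compare this to the prognoses obtained from cases where USS identified isolated mild VM". Objective 1b of Project 3 in section 2 names the same comparison. Neither place mentions a population rate.
- **Sample size Project 3** (section 7): "With approximately 140 cases and assuming the prevalence of poor outcome is indeed less than 10" per cent, "we will be able to estimate the prevalence to within a standard error of 2.5" per cent.
- **Prognosis scale** (main protocol, section 3, Secondary Outcomes): "favourable - greater than 90% chance of normal outcome". The next category down, intermediate, is 50-90%.
- **Usual prognosis** (follow-up section 6, Project 3): "the most common information given to women on the basis of isolated mild VM on USS is" the favourable (90%) category.
- **Outcome scale** (follow-up section 6, Project 2): children are classed as "severely impaired (scoring <70), mild-moderately impaired (scoring 70-85) or normal (scoring 85" or more). Section 2 sets the same BSID cut-off beside a standard-deviation band on the ASQ: "non-severe impairment (defined as BSID <85 or a score between 1 and 2 SDs for the ASQ".

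**The concern.** The hypothesis and the analysis have different comparators. The hypothesis asks about excess risk over ordinary children. The analysis sets the observed prevalence beside what clinicians predicted, and those predictions are on a scale where normal is a clinical judgement. The outcome's normal is a cut-off on a standardised test, which by construction some unaffected children miss.

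Project 3 is meant to establish the clinical significance of isolated mild ventriculomegaly. If the share scoring below 85 is read straight against a prognosis of over 90% normal, the background rate of low scores is counted against the condition. The report could then suggest that women given a favourable prognosis were told something too optimistic, when their children were developing like any others.

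**Working it through.** **1. The plan's own figure.** SE = sqrt(p(1-p)/n). With p = 0.10 and n = 140: sqrt(0.09/140) = 2.54%. The stated 2.5% reproduces (it is exact at n = 144).

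**2. Share of unaffected children below 85.** The documents call BSID scores standardised but give no mean or SD. Assumption: mean 100, SD 15, normal scores, so 85 is 1 SD below the mean. The pairing of 85 with the 1-2 SD band in section 2 suggests this but does not prove it. The share is then P(Z < -1) = 15.9%, leaving an 84% chance of normal. On the main protocol's prognosis scale that is intermediate, not favourable.

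Varying one assumption at a time:

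| Assumed norm | Share below 85 |
|---|---|
| mean 100, SD 13 | 12.4% |
| mean 100, SD 15 | 15.9% |
| mean 100, SD 16 | 17.4% |
| mean 105, SD 15 | 9.1% |

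If a low score on any of three indices counted, the share would be about 26-34% (assumed correlations 0.8 down to 0.4).

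**3. What 140 children with no excess risk would show.** The expected number below 85 is 140 x 0.159 = 22. The observed share exceeds 10% when at least 15 score below 85. The exact (Clopper-Pearson) 95% lower limit exceeds 10% when at least 22 do (22/140 gives 10.1% to 22.8%).

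| True share below 85 | P(observed > 10%) | P(exact lower limit > 10%) |
|---|---|---|
| 10% | 0.43 | 0.022 |
| 9.1% (mean 105) | 0.30 | 0.008 |
| 15.9% (mean 100, SD 15) | 0.97 | 0.56 |
| 17.4% (SD 16) | 0.99 | 0.74 |

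**4. The same data against the right reference.** If the comparator is the 15.9% norm itself, the lower limit exceeds it with probability 0.019 when there is no excess risk. The apparent failure in step 3 comes from the comparator.

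**5. Does the planning value of under 10% hold for severe impairment?** The document has two definitions.
- Score below 70 (section 6 categories; headings of the section 7 table): P(Z < -2) = 2.3% of ordinary children. The planning value holds, and SE = sqrt(0.0228 x 0.9772/140) = 1.3 points.
- Cognitive and language both below 80, or combined below 85, or motor below 70 (sections 2 and 7, text): reading combined as the mean of the two indices, simulation with correlations 0.4-0.8 puts about 13-15% of ordinary children in this group. The planning value may then fail, and the SE is 2.8-3.0 points.

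**6. Precision for any impairment.** At 15.9%, SE = sqrt(0.159 x 0.841/140) = 3.1 points.

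**The case against.** A reader might infer that Project 3 judges its results against a 10% benchmark. The documents do not support that. The 10% appears once, as a planning value for a standard error that is computed correctly. No threshold, null value or decision rule uses it, and its link to the favourable category is only suggested by the sentence's wording.

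It can also be said that the hypothesis already names the general population, and that section 7 pairs poor prognosis mainly with severe impairment, treating the 70-85 band as secondary. Both are true, and they limit the point. They do not remove it. The analysis as written never makes the population comparison. It covers non-severe impairment as well, and the secondary tabulation in section 7 pairs normal or favourable prognoses with scores above 85. A numerical reference rate could reasonably be left to a statistical analysis plan, but the mismatch between hypothesis and stated analysis is in the protocol.

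Two further readings go too far. One is that unaffected children would be certain to refute the favourable prognosis: an interval wholly above 10% has probability 0.56 under the main assumption, and 0.008 if the mean is 105. The other is that comparing severe impairment with 10% is a defect because it hides a two- or three-fold excess. A prognosis of over 90% normal is not contradicted by 4.6% or 6.8% severe impairment. Excess over the population is a separate question, which the hypothesis asks; at three times a 2.3% norm the exact lower limit would exceed that norm with probability 0.75.

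**Conclusion.** The point stands in a limited form. Project 3's stated analysis does not test its stated hypothesis, and the comparator it does use ignores the background rate of low scores. If 85 is 1 SD below the norm, about 16% of unaffected children miss follow-up normal. With 140 of them the observed share below 85 would then almost always exceed 10% (0.97), and the interval would exclude 10% slightly more often than not (0.56).

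The size depends on norms that the documents do not state. If the mean has drifted up to 105 the share is 9.1% and the misleading result largely disappears, although background low scores would still use up nearly all of the 10% that a favourable prognosis leaves. The sample-size sentence is arithmetically sound. Whether its assumption of under 10% is safe turns on which definition of severe impairment applies.

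**What to change.** **In Analysis of Project 3:** add, as the test of the stated hypothesis, a comparison of each prevalence (with its exact 95% interval) against the standardisation-population rate for the same cut-off or composite rule. For a single index under the assumed norms these rates are about 2.3% below 70 and 15.9% below 85. Keep the comparison with prognoses, but do not read the share below 85 directly against a prognosis of over 90% normal without that base rate.

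**Definitions:** define poor outcome for Project 3, and reconcile the below-70 definition of severe impairment with the composite one in sections 2 and 7.

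**In Sample size Project 3:** state precision per outcome, about 1.3 points at 2.3% and about 3.1 points at 15.9%, or the figure for the composite rule if that is kept.

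**Cost:** wording and one reference rate per outcome, with no new children or data. The stated precision for any impairment becomes slightly worse (3.1 instead of 2.5 points). The comparison inherits any uncertainty in the norms, so a short sensitivity range is sensible.

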Appendix 1 - Developmental assessments

A full assessment will require determination of developmental, sensory, psychomotor and behavioural functioning. We propose to use validated parent completed questionnaires (GMFCS and SDQ) [16-17] where it is not possible to arrange a face to face assessment in order to minimise loss to follow up. These can also be completed via telephone if paper copies are not returned. This is an important and pragmatic approach because it allows us to minimise loss to follow up, whilst robustly determining the true proportion of children with a severe impairment. A face to face assessment will take between 1 and 2 hours and will be completed by a suitably trained paediatrician, physiotherapist or other health professional, and will include:

- BSID III [15] – mental and psychomotor developmental index; time 30-60 minutes.
- Motor function – BSID III and GMFCS [16]; time 5 minutes
- Sensory impairment – parent reported use of hearing or visual aids: time <5 minutes
- Behaviour – SDQ [17] a brief behavioural screening questionnaire which consists of 25 questions

The primary outcomes will be based on BSID III [15], supplemented where necessary by the ASQ [14], and give the proportion of infants surviving without mild, moderate or severe disability at 3 years. This data will be supplemented by using validated questionnaires (GMFCS and SDQ) [16-17] comprising forced-choice items to assess sensory impairment and standardised measures to assess motor and cognitive function and to identify children with:

- Mild/moderate/severe vision or hearing impairment
- Any motor impairment (cerebral palsy with GMFCS level 2)/severe motor impairment (cerebral palsy with GMFCS level 3, 4 or 5)
- Moderate/severe cognitive impairment will also be assessed using ASQ [14] which is a well validated widely used tool appropriate for children at this age, and is easily completed by parents.

Definitions for motor and sensory impairments described above are as defined by British Association of Perinatal Medicine (BAPM 2008).

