- b. Measurement of diagnostic accuracy of in utero MR (following antenatal US) relative to the updated reference diagnosis at 2-3 years of age (postnatal imaging or post-mortem examination).

Further details of methods and analyses are available in the MERIDIAN protocol [1].

The impact of non-consent to follow-up is anticipated to be very small and will not directly influence the power of the study. All MERIDIAN cases will be retained (using original diagnosis if no consent is received); meaning that the effective sample size is likely to increase where the additional follow-up yields data where previously none was available.

Sample size Project 1

The original MERIDIAN study requires data on 336 children to detect a 10% improvement in diagnostic accuracy. We anticipate the number of participants consenting to repeat examination will be much greater than 336, and the improvement in diagnostic accuracy to be greater still than 10% due to better quality reference data.

Analysis of Project 2

Results from the BSID will allow us to determine the developmental outcome and categorise as; severely impaired, mild-moderately impaired or normal. For the purpose of this analysis, we will consider a severely impaired neuro-developmental outcome as being one where:

- i) The BSID psychomotor component is below 70 (physical impairment)
- ii) The BSID score of <80 on the Cognitive AND language index
- iii) The cognitive and language index has a combined score of <85
- iv) Cerebral palsy on GMFCS
- v) Where there was no BSID assessment, but where the ASQ is <2 SDS below the mean corrected for age

The primary analyses will focus on this as a dichotomous outcome (severe impairment: yes/no). Secondary analyses will further assess whether the prognoses also differentiate children with a BSID of between 70 and 85 (which we tentatively term "mild to moderate impairment") from those with unequivocally normal development (85 or above). We will also assess the actual range of scores within each prognostic category.

There are two primary (and sequential) considerations:

- 1) To quantify the value of prognoses based on MR and on USS
- 2) To assess whether the prognostic value of MR increases relative to that of USS

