The first consideration is a pre-cursor to the second, since the comparison in 2) is irrelevant if neither MR nor USS contain some measure of useful prognostic information. We will quantify 1) by assessing the concordance between severe neurodevelopmental impairment (BSID score of <80 on the Cognitive AND language index or a combined score of <85 or a motor score of <70) and poor prognosis, based on i) MR and ii) USS. The sensitivity, specificity, positive and negative predictive values of MR and of USS will be reported.

The second consideration is to compare the relative prognostic accuracy of USS and MR. We will do so by calculating the difference in the respective sensitivities and specificities using the paired sample methods recommended by Newcombe [18].

	Outcome	
	Severe impairment (BSID<70) N=xxx	No severe impairment (BSID>=70) N=xxx
USS prognosis		
Poor	n (%)	n (%)
Normal/favourable	n (%)	n (%)
% correctly classified*	$P_{sens (USS)}$	$P_{spec (USS)}$
MR prognosis		
Poor	n (%)	n (%)
Normal/favourable	n (%)	n (%)
% correctly classified*	$P_{sens (MR)}$	$P_{spec (MR)}$
Difference (95% CI)	$P_{sens (MR)} - P_{sens (USS)}$	$P_{spec (MR)} - P_{spec (USS)}$
P-value (McNemar)		

* Here, we consider "Correct" to mean 1) Poor prognosis corresponds to severe impairment, and 2) Normal/favourable prognoses correspond to no severe impairment. The percentages correctly classified reflect 1) sensitivity and 2) specificity respectively.

The secondary outcomes are

- 3) To assess qualitatively the cases for which the USS prognosis and MR prognosis differed, in relation specifically to the original diagnoses
- 4) To look at the concordance in the subgroup of children for which the MR scan was performed within 24 weeks
- 5) To assess ability to predict non-severe impairment

The last of these will further subdivide children without severe impairment (BSID>=70) into "mild-moderate impairment" (BSID between 70 and 85) and "Normal" (BSID>85). The corresponding prognostic categories are "Intermediate" and "Normal or Favourable", and the concordance between the three prognostic categories and the three outcomes will be reported by two-way tabulations.

Sample size Project 2

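### Project 2's severe-impairment outcome has conflicting cut-offs, and under the section 7 list the BSID and ASQ limbs sit at different severities

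*Protocol*

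**What the plan says.** All references are to the 2-3 year follow-up protocol.

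- **Role of the outcome.** Section 7 (Analysis of Project 2) makes severe impairment, yes or no, the focus of the primary analyses. Appendix 1 adds "The primary outcomes will be based on BSID III [15], supplemented where necessary by the ASQ [14". (Appendix 1 swaps the two citation numbers: in the reference list 14 is the Bayley scales and 15 is the ASQ.)
- **BSID limb.** Section 2, objective 1a: "defined by BSID score of <80 on the Cognitive AND language index or a combined score of <85 or a motor score of <70". Section 7 lists the same limbs, including "The BSID psychomotor component is below 70 (physical impairment" and "The cognitive and language index has a combined score of <85", and its concordance paragraph repeats them.
- **ASQ limb.** Section 2, objective 1a: "evidence of severe disability based on a score <-2SDs for the ASQ". Section 7, item v: "Where there was no BSID assessment, but where the ASQ is <2 SDS below the mean corrected for age". I read item v in the sense of objective 1a, as more than 2 SD below the mean.
- **Non-severe impairment.** Section 2, objective 4: "defined as BSID <85 or a score between 1 and 2 SDs for the ASQ".
- **A second BSID cut-off.** Section 6 (Project 2) grades children as severe below 70, mild-moderate from 70 to 85 and normal from 85. The results table in section 7 also splits severe from not severe at BSID 70, and the secondary analysis there uses the 70 to 85 band.
- **GMFCS limb.** Cerebral palsy on the GMFCS also counts as severe, with either instrument.

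**The concern.** One dichotomous outcome has two entry rules, and which rule applies depends on whether a BSID was done. If the rules sit at different severities, the label reflects attendance, consent and age as well as development.

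Children without a BSID arise by design and not at random. Project 2, which contains the BSID, is optional (section 5). Children over 38 months get no developmental assessment but stay in Project 1 (section 4), and the ASQ is sent out with the Project 1 consent papers (section 5). An ASQ returned without a consent form is still used (section 5). Some appointments will be missed, and a few children with very complex impairments cannot do a BSID (section 6).

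At stake are the prevalence of severe impairment, the absolute sensitivity, specificity and predictive values of each prognosis, and the Project 3 prevalence, which uses the Project 2 categories.

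**Working it through.** **The plan's own figure.** The only sample-size statement tied to this outcome is 90% power with 400 cases for a 20% gain in sensitivity and 10% in specificity, two-sided 5% (section 7). It cannot be reproduced, because neither the number of severe cases nor the discordance psi within each outcome group is given. Reading the gains as percentage points d, the paired formula n = (z_a·sqrt(psi) + z_b·sqrt(psi − d²))² / d² gives:

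- sensitivity, d = 0.20: 49 severe cases at psi = 0.20, up to 122 at psi = 0.48;
- specificity, d = 0.10: 101 non-severe cases at psi = 0.10, up to 417 at psi = 0.40.

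The stated power is neither confirmed nor disputed here.

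**Step 1: the scale.** The documents state no BSID mean or SD. Objective 4 with the 70 to 85 band suggests 85 = −1 SD and 70 = −2 SD. Then SD = 85 − 70 = 15 and mean = 85 + 15 = 100. This is an assumption.

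**Step 2: each cut-off**, with z = (cut-off − 100)/15 and the normal tail area.

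| Limb | z | Share of reference population |
|---|---|---|
| Combined <85 | −1.00 | 15.9% |
| A single index <80 | −1.33 | 9.1% |
| Motor <70 | −2.00 | 2.3% |
| ASQ beyond 2 SD | −2.00 | 2.3% |

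Motor <70 already matches the ASQ. The mismatch comes from the combined limb and, less so, the limb requiring both indices below 80. If the instruments agree perfectly, the children classed differently are those between −2 and −1 SD: 15.9% − 2.3% = 13.6%.

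**Step 3: the whole BSID rule.** Cognitive, language and motor scores were simulated for 2,000,000 children with common correlation 0.3 to 0.9, and a child was flagged on any of the three BSID limbs.

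- Combined score taken as a plain average: 12.2% to 15.3% flagged.
- Combined score re-standardised to SD 15: 15.9% to 17.1% flagged.

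Overall that is about 12-17%, against 2.3% on the ASQ: a ratio of roughly 5 (12.2/2.28 = 5.4) to 7.5 (17.1/2.28).

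**Step 4: cut-off or measurement noise?** This step compares one BSID score at −1 SD with one ASQ score at −2 SD. At correlations of 0.5 to 0.9 between instruments, 13.6% to 14.5% of children are severe on BSID only and at most 0.9% on ASQ only. With both cut-offs at −2 SD, total disagreement is 1.9% to 3.7%. Most of the difference therefore comes from the cut-offs.

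**Step 5: a lower cohort mean** (assumed, perfect agreement).

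- 0.5 SD lower: 30.9% − 6.7% = 24.2% classed differently.
- 1 SD lower: 50.0% − 15.9% = 34.1%.

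**Step 6: the passages side by side.** A BSID score below 85 appears under severe (objective 1a and section 7, for the combined cognitive-language score) and under non-severe (objective 4, where the score is unspecified). Severe is also BSID below 70 in section 6 and in the section 7 table. These cannot all hold.

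**The case against.** **Which definition governs is itself unsettled.** If BSID below 70 governs, as in section 6 and the section 7 table, both limbs sit at 2 SD on the assumed scale and the instrument mismatch disappears. This stands. The contradiction is certain; the mismatch follows under objective 1a and the section 7 list. That list is, however, the one stated to define severe impairment for the analysis, and the concordance paragraph repeats its BSID limbs.

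**SD units do not prove equal severity.** A clinician-administered test and a parent questionnaire may differ at the same nominal SD. The amendment summary says that BSID scores were updated for BSID III, so these cut-offs were revised for that instrument. Objective 4 is part of the conflicting drafting and is weak evidence of calibration. This stands as a limit on the numbers. Still, the protocol gives no calibration and no reason for pairing 85 with 2 SD.

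**The combined score is undefined.** On either version simulated, both indices below 80 always implies combined below 85, so that limb is redundant. This casts some doubt on the reading, and is one more thing to clarify.

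**A reader might infer that a known share of severe cases is lost.** The documents do not support such a count. They give neither the ASQ-only share nor the cohort's score distribution. Section 7 also counts non-survivors, expected to number 50-100, as poor outcomes, and the GMFCS limb can capture some children who have no BSID.

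**A reader might infer that the MR-ultrasound comparison is biased.** Both prognoses are judged against the same outcome in the same child by paired methods, so the documents do not show this. Nor do they show that BSID uptake differs by the prognosis given. Section 7 plans to compare the prognoses and diagnoses of consenters and refusers, which partly addresses selective participation but not the unequal cut-offs.

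**Conclusion.** The point holds in this form: severe impairment, the Project 2 primary outcome, is defined inconsistently across sections 2, 6 and 7, and under the section 7 list the label depends on which instrument was completed. Between about −2 and −1 SD a child is severe with a BSID and not severe with only an ASQ. The BSID rule flags about 12-17% of a reference population and the ASQ rule 2.3%.

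These figures assume mean 100, SD 15, normal scores, a single ASQ score, and a combined score that is an average or its re-standardised form. How far the reported results move depends on the share of ASQ-only children, which is unknown. That share also depends on whether Project 1-only families enter the Project 2 analysis; item v in section 7 does not exclude them.

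Prevalence, absolute sensitivity, specificity and predictive values, and Project 3 prevalence are affected. A bias in the paired MR-ultrasound difference is not established. This should be corrected. It is not a detail left to an analysis plan, because the protocol itself fixes the conflicting thresholds.

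**What to change.** 1. Reconcile objectives 1a and 4 (section 2), the categories in section 6, and the list, concordance text and table in section 7 into one definition of severe impairment. Which threshold to adopt is for the investigators.
2. State the BSID and ASQ limbs at the same pre-specified severity standard, define the combined score, and word the direction of the ASQ cut-off clearly.
3. Add a sensitivity analysis restricted to children with a BSID, and report the severe rate by instrument for Projects 2 and 3.
4. If the ASQ cut-off is calibrated in children who have both instruments, keep that as a sensitivity analysis at most. It would be data-driven and would rest on families who attended.

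The cost is wording changes in sections 2, 6 and 7 and Appendix 1, plus one small extra analysis on data already to be collected.
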